#### For all subjects:

Across the two treatment groups in this study, intensity, duration, and frequency of intensive arm motor therapy will be carefully matched. The content of therapy will be standardized via use of specific study protocols, which are modeled after two main sources: *Upper-Extremity Task-Specific Training After Stroke or Disability* (Lang and Birkenmeier) and the *Accelerated Skill Acquisition Program* from the Interdisciplinary Comprehensive Arm Rehabilitation Evaluation study. In both treatment groups, therapy will include stretching, exercises, and functional training. Feedback, review of progress, and treatment plan revisions will be regularly shared with the study subject. All activities during the 6 weeks of therapy (treatment supervision, assessments, education) will be performed/overseen by one of the site's Treatment Therapist; the site's Assessment Therapists will not be involved with enrollees in any way during the 6 weeks of therapy. For a given patient, across the 6 weeks of study-related therapy, all treatment should be provided by the same Treatment Therapist, as reasonably possible.

Within 10 days of the Baseline Visit (target value < 5 days), all subjects will begin a 6-week regimen of study-designated intensive arm motor therapy (in-clinic vs. telerehabilitation). Prior to the first day of therapy, the Treatment Therapist will use the study manual of procedures to plan the specific content and details of therapy, incorporating subject data acquired at the Screening and Baseline Visits. The Treatment Therapist will revise this treatment plan twice thereafter (after 6 supervised sessions and again after 12 supervised sessions).

#### Therapy:

During each of the ensuing six weeks, all subjects will receive 6 therapy sessions/week, 3 of which will be supervised and 3 of which will be unsupervised. **Each subject will therefore receive a total of 36 therapy sessions**, consisting of **18 supervised therapy sessions** (Monday/Wednesday/Friday, when possible) **and 18 unsupervised therapy sessions** (Tuesday/Thursday/Saturday, when possible) as part of study participation. Each treatment session will be 80 minutes long, including a brief break. Interruptions in this schedule may be unavoidable in some cases, e.g., due to illness or during a holiday. When a supervised therapy session is missed, the study team will schedule a make-up supervised session for the subject. The goal is to have supervised sessions alternate with unsupervised sessions, but this is not required. Similarly, if a subject cannot perform an unsupervised therapy session on an assigned date, a make-up unsupervised session will be scheduled. The study will allow up to 8 weeks for completion of the 36 therapy sessions.

Subjects will be told that, if at any point during an unsupervised session a concern arises or a question comes up, they should wait until the next supervised session to ask the therapist if at all possible, but if the question is urgent they may call the study site. All such calls will be documented.

#### Assessments:

All subjects will undergo a brief set of assessments during the third supervised therapy session then again every 3 supervised sessions until the end of therapy. These assessments will record adverse events (which includes study-related adverse events, serious adverse events, and interval medical history), ascertain subject compliance with the unsupervised therapy sessions, document any new medications, and document the amount of any therapy (OT, PT, SLT) that the subject received outside of study procedures. At the end of supervised sessions 6 and 12, the subject will be briefly asked about any new interval medical history events. In addition, at the end of supervised session 3 and supervised session 18, the PACES, OPS scale, and Patient Satisfaction Questionnaire will each be completed. These brief assessments will be performed by the subject's Treatment Therapist.

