### 5.3. Data Collection Schedule

Case Report Form	Screening	Baseline	End of 3 Supervised Sessions	End of 6 Supervised Sessions	End of 9 Supervised Sessions	End of 12 Supervised Sessions	End of 15 Supervised Sessions	End of 18 Supervised Sessions	Post-therapy	30 Day Follow Up	End of Study
Obtain Informed Consent	X										
Eligibility criteria	X										
Medical History	X										
Arm Motor Fugl-Meyer Scale	X	X							X	X	
Box & Blocks Test	X								X	X	
Montreal Cognitive Assessment	X										
Geriatric Depression Scale	X										
modified Ashworth Spasticity Scale(wrist)	X										
Nottingham Sensory Scale	X										
Blood Pressure & Weight	X									X	
modified Rankin Scale	X									X	
NIH Stroke Scale	X										
Stroke Knowledge Exam	X								X		
Non-study rehabilitation therapy	X	X	X	X	X	X	X	X	X	X	
(Pre-Stroke) Handedness Inventory		X									
Prior and Concomitant Medications	X	X	X	X	X	X	X	X	X	X	
Stroke Impact Scale-Hand Subsection		X							X	X	
Physical Activity Enjoyment Scale (PACES)		X	X					X			
Optimization in Primary and Secondary Control Scale (OPS)		X	X					X			
Randomization		X									
Patient Satisfaction Questionnaire			X					X			
Adverse Events			X	X	X	X	X	X	X	X	
Therapy Compliance			X	X	X	X	X	X			
End-of-Study Form											X

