**5.3.3.1 Additional details for subjects randomized to in-clinic therapy:**

The 18 supervised therapy sessions will take place at the central study site. A Treatment Therapist will provide continuous supervision throughout each of these 80 minute treatment sessions. A revised treatment plan will be generated and implemented after 6 supervised sessions and again after 12 supervised sessions of therapy.

The 18 unsupervised therapy sessions will take place in the patient's home, and will be guided by an individualized booklet generated and printed by the Treatment Therapist and distributed to the subject during the first in-clinic therapy visit. The content of the unsupervised therapy sessions will be matched to the same exercise and training components provided during the subject's in-clinic supervised therapy sessions. After 6 supervised sessions and again after 12 supervised sessions of therapy, the booklet guiding the unsupervised therapy session will be returned to the therapist, at which time a new booklet will be provided to the subject, containing a revised therapy plan. At the start of each of the 18 unsupervised sessions, all subjects will receive 5 minutes of stroke education. As with the other content of the unsupervised sessions, stroke education will be delivered by booklets provided by the Treatment Therapist during a supervised therapy session. Using a large Helvetica font, a multiple-choice question is presented, the patient marks his/her answer, then the patient is provided with the correct answer along with a brief explanation. This is repeated four times, for a total of five questions at each unsupervised session.

If there are any unsupervised therapy sessions completed after a subject's final supervised therapy session, the Treatment Therapist will call the patient at home and collect data on compliance for any such sessions.

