**5.3.3.2 Additional details for subjects randomized to telerehabilitation therapy:**

A member of the study team will deliver the telerehabilitation system to the subject's home, set it up, confirm functionality, and review use of the system with the subject. Note that the telerehabilitation system will not operate for any process apart from telerehabilitation at any time, and will only provide telerehabilitation for the number of assigned minutes.

The 18 supervised therapy sessions will be performed by the subject, at home, using the telerehabilitation system. At the beginning of each supervised session, a Treatment Therapist at the central study site will initiate a videoconference with the subject's telerehabilitation system.

The Treatment Therapist will then supervise the subject, using a structured approach, for a 30 minute period during which the therapist will observe the patient performing assigned home-based telerehabilitation exercises and tasks, answer questions, review the treatment plan, and perform the brief study assessments during selected days. After 30 minutes, the therapist will disconnect from the videoconference, then the subject will complete the remaining 50 minutes of therapy, including a brief break, guided by the telerehabilitation system.

The 18 unsupervised therapy sessions will also be performed by the subject at home using the telerehabilitation system. There will be no contact with a study therapist during these sessions. Instead, all 80 minutes of therapy will be guided only by the telerehabilitation system. At the start of each of the 18 unsupervised sessions, subjects in the telerehabilitation group will receive 5 minutes of stroke education. As with the other content of the unsupervised sessions, stroke education will be delivered by the telerehabilitation system. A 5-level multiple-choice question is presented on the computer screen, the patient enters his/her answer, and then the patient is provided with the correct answer along with a brief explanation. This is repeated four times, for a total of five questions at each unsupervised session. All steps (read, answer, move forward, etc.) are timed, recapitulating the approach used successfully in our pilot study.

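### PACES is due at the end of supervised sessions 3 and 18, but the telerehabilitation therapist leaves after 30 of 80 minutes, so its timing probably differs by arm

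*Combined protocol and SAP*

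**What the plan says.** Three parts of the protocol place the PACES, OPS and Patient Satisfaction Questionnaire at the end of a session. Section 5.3.3 (Assessments) states that "at the end of supervised session 3 and supervised session 18, the PACES, OPS scale, and Patient Satisfaction Questionnaire will each be completed", and closes with "These brief assessments will be performed by the subject's Treatment Therapist". The Data Collection Schedule in section 5.3 heads the relevant column "End of 3 Supervised Sessions", with a matching column for session 18. Section 8.5 describes PACES as scored after 3 and after 18 supervised sessions.

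Session conduct differs by arm. Section 5.3.3 (Therapy) says that "Each treatment session will be 80 minutes long, including a brief break". For the in-clinic arm, section 5.3.3.1 says that "A Treatment Therapist will provide continuous supervision throughout each of these 80 minute treatment sessions". For telerehabilitation, section 5.3.3.2 opens each supervised session with a 30-minute videoconference, in which the therapist is to observe exercises and also to "answer questions, review the treatment plan, and perform the brief study assessments during selected days". It continues: "After 30 minutes, the therapist will disconnect from the videoconference". The subject then finishes the session guided by the system.

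Aim 1.3.2 and section 8.5 compare the change in PACES between arms by ANCOVA, from baseline to the end of week 1 (primary) and to the end of week 6 (secondary). The model controls for days from stroke onset to randomization, baseline PACES, age and site.

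**The concern.** In the telerehabilitation arm the therapist cannot perform PACES at the end of the 80-minute session and also perform it within the first 30 minutes. A site that follows section 5.3.3.2 for telerehabilitation and the Assessments text for in-clinic therapy would rate one arm after a complete session and the other before most of that session's therapy.

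PACES asks how much the subject enjoys the therapy. A rating given straight after 80 minutes of intensive arm work might differ from one given early in the session, through fatigue or recency. If timing follows arm, none of the planned covariates can separate it from a treatment difference. The comparison at stake is the Aim 1.3.2 test of activity-inherent motivation. PACES also enters the OPS x PACES interaction in the compliance analysis of section 8.5.

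**Working it through.** **Passages side by side**

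| Item | In-clinic | Telerehabilitation |
|---|---|---|
| Session length (5.3.3, Therapy) | 80 min | 80 min |
| Therapist present (5.3.3.1, 5.3.3.2) | all 80 min | first 30 min |
| Stated point for PACES (5.3, 5.3.3 Assessments, 8.5) | end of, or after, the session | end of, or after, the session |
| Point at which the therapist can do it live | any point, including minute 80 | at or before minute 30 |

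**The plan's own figure.** Session length minus supervised time is 80 - 30 = 50 minutes, which matches the remaining time given in section 5.3.3.2. It includes any break that falls in that part of the session.

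**Gap relative to scheduled therapy.** Let s be the number of the supervised session at which PACES is taken and u the number of unsupervised sessions already completed.

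- In-clinic minutes before PACES = (s + u) x 80
- Telerehabilitation minutes before PACES, at most = (s - 1 + u) x 80 + 30
- The difference is 50 minutes in every case

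The main case assumes the alternating schedule that the protocol aims for, so u = s - 1. The other two rows vary that assumption.

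| Supervised session | u | In-clinic (min) | Telerehabilitation (min) | Gap |
|---|---|---|---|---|
| 3 | 2 (alternating) | 400 | 350 | 50/400 = 12.5% |
| 3 | 3 | 480 | 430 | 50/480 = 10.4% |
| 3 | 0 (supervised only) | 240 | 190 | 50/240 = 20.8% |
| 18 | 17 (alternating) | 2800 | 2750 | 50/2800 = 1.8% |
| 18 | 18 | 2880 | 2830 | 50/2880 = 1.7% |
| 18 | 0 (supervised only) | 1440 | 1390 | 50/1440 = 3.5% |

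**Which analyses use the affected scores.** Section 8.5 compares PACES change between arms and uses PACES in the OPS x PACES term. The OPS hypothesis uses the Baseline Visit score, which is taken before any therapy. Section 8 specifies no analysis of the Patient Satisfaction Questionnaire. The Fugl-Meyer primary endpoint is scored by the blinded Assessment Therapist at separate visits.

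**The case against.** The strongest reply is that the arm difference is inferred, not stated. The Assessments text first says "All subjects will undergo a brief set of assessments during the third supervised therapy session then again every 3 supervised sessions", listing adverse events, compliance, medications and outside therapy, and only then adds the three scales. The telerehabilitation text could refer to the first set alone. Section 5.3.2 has the therapist provide PACES and OPS to the subject, and section 5.3.3 allows assessments to be overseen as well as performed, so self-completion after the therapist disconnects is conceivable. The manual of procedures, which is not among the documents, may fix the point. All this makes the arm difference likely, not certain. It does not reconcile the sections: the sentence on who performs the brief assessments follows directly on the three scales, and no reconnection or later completion is described for them. By contrast, section 5.3.3.1 does spell out a telephone call for late compliance data. Taking the end of the session to mean the end of the videoconference does not help either, because the arms would still be 50 minutes apart.

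It is also fair that the endpoint is defined on the scale of weeks, and that 50 minutes is modest against cumulative therapy, especially at session 18. That limits the importance of the point.

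A reader might go further and infer that the OPS and satisfaction results are compromised in the same way. The documents do not support that: the OPS predictor is the baseline score, and no satisfaction comparison is planned. A reader might also want to state how far the false-positive rate of the PACES test is raised. That needs a PACES standard deviation and a size for the timing effect, and the documents give neither. Nor do they say that PACES responds to fatigue or recency within a session.

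**Conclusion.** The timing instructions for PACES conflict between section 5.3.3 (Assessments), supported by sections 5.3 and 8.5, and section 5.3.3.2. On the most natural reading, in-clinic subjects are rated at about minute 80 and telerehabilitation subjects at or before minute 30 of the same numbered session. This rests on two assumptions: that the brief assessments in section 5.3.3.2 include PACES, and that no unseen manual sets another route. A claim that timing is certainly and wholly confounded with arm would go beyond the text.

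The difference is 50 scheduled minutes, or about 12.5% of prior therapy at session 3 and about 2% at session 18. Any resulting bias in the PACES comparison is of unknown direction and size. The effect is confined to PACES and possibly the OPS x PACES analysis. The primary endpoint and the sample size of 124 are not affected. The priority is minor, but the remedy is inexpensive, and no planned covariate could correct a timing difference afterwards.

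**What to change.** Reconcile section 5.3.3 (Assessments) with section 5.3.3.2 so that PACES is given at the same elapsed point and in the same mode in both arms. For consistency, treat OPS and the Patient Satisfaction Questionnaire in the same way.

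The simplest choice is within the first 30 minutes of supervised sessions 3 and 18 in both arms. The timing wording in the section 5.3 schedule, section 5.3.3 and section 8.5 would need to change to match. This adds no visit and no staff. Its cost is that the rating comes before the rest of that session's therapy in both arms.

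The alternative is self-completion at the end of the 80 minutes in both arms. This keeps the end-of-session definition. If the questionnaires were shown on the telerehabilitation system, section 5.3.3.2 would also have to be amended, because it confines the system to telerehabilitation and to the assigned minutes, and some software work would probably follow.

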**Stroke education:**

At the start of each of the 18 unsupervised sessions, all subjects will receive 5 minutes of stroke education. The information presented corresponds to the content of the Stroke Knowledge Exam, which focuses on prevention, recognition, response, and management of stroke. Subjects assigned to in-clinic therapy will review the stroke education booklet. Subject assigned to telerehabilitation will receive this information via the telerehab system.

**5.3.3.1 Additional details for subjects randomized to in-clinic therapy:**

The 18 supervised therapy sessions will take place at the central study site. A Treatment Therapist will provide continuous supervision throughout each of these 80 minute treatment sessions. A revised treatment plan will be generated and implemented after 6 supervised sessions and again after 12 supervised sessions of therapy.

The 18 unsupervised therapy sessions will take place in the patient's home, and will be guided by an individualized booklet generated and printed by the Treatment Therapist and distributed to the subject during the first in-clinic therapy visit. The content of the unsupervised therapy sessions will be matched to the same exercise and training components provided during the subject's in-clinic supervised therapy sessions. After 6 supervised sessions and again after 12 supervised sessions of therapy, the booklet guiding the unsupervised therapy session will be returned to the therapist, at which time a new booklet will be provided to the subject, containing a revised therapy plan. At the start of each of the 18 unsupervised sessions, all subjects will receive 5 minutes of stroke education. As with the other content of the unsupervised sessions, stroke education will be delivered by booklets provided by the Treatment Therapist during a supervised therapy session. Using a large Helvetica font, a multiple-choice question is presented, the patient marks his/her answer, then the patient is provided with the correct answer along with a brief explanation. This is repeated four times, for a total of five questions at each unsupervised session.

If there are any unsupervised therapy sessions completed after a subject's final supervised therapy session, the Treatment Therapist will call the patient at home and collect data on compliance for any such sessions.

**5.3.3.2 Additional details for subjects randomized to telerehabilitation therapy:**

A member of the study team will deliver the telerehabilitation system to the subject's home, set it up, confirm functionality, and review use of the system with the subject. Note that the telerehabilitation system will not operate for any process apart from telerehabilitation at any time, and will only provide telerehabilitation for the number of assigned minutes.

The 18 supervised therapy sessions will be performed by the subject, at home, using the telerehabilitation system. At the beginning of each supervised session, a Treatment Therapist at the central study site will initiate a videoconference with the subject's telerehabilitation system.

The Treatment Therapist will then supervise the subject, using a structured approach, for a 30 minute period during which the therapist will observe the patient performing assigned home-based telerehabilitation exercises and tasks, answer questions, review the treatment plan, and perform the brief study assessments during selected days. After 30 minutes, the therapist will disconnect from the videoconference, then the subject will complete the remaining 50 minutes of therapy, including a brief break, guided by the telerehabilitation system.

The 18 unsupervised therapy sessions will also be performed by the subject at home using the telerehabilitation system. There will be no contact with a study therapist during these sessions. Instead, all 80 minutes of therapy will be guided only by the telerehabilitation system. At the start of each of the 18 unsupervised sessions, subjects in the telerehabilitation group will receive 5 minutes of stroke education. As with the other content of the unsupervised sessions, stroke education will be delivered by the telerehabilitation system. A 5-level multiple-choice question is presented on the computer screen, the patient enters his/her answer, and then the patient is provided with the correct answer along with a brief explanation. This is repeated four times, for a total of five questions at each unsupervised session. All steps (read, answer, move forward, etc.) are timed, recapitulating the approach used successfully in our pilot study.

A revised treatment plan for the supervised and for the unsupervised therapy sessions will be generated and implemented after 6 supervised sessions and again after 12 supervised sessions of therapy, by the Treatment Therapist at the study site, then uploaded through the internet to the telerehabilitation system in the subject's home. Within 3 days of the last telerehabilitation therapy session, a member of the site study team will remove the telerehabilitation system from the subject's home.

#### **5.3.4 Post-Therapy Visit**

Immediately after the end of therapy (1-6 days following last day of therapy, target value = 2 days), the subject will return to the central study site for testing. The study site will call the subject the day before this visit, reminding him/her of the time and place of the visit. All testing during the Post-Therapy Visit will be performed by one of the site's Assessment Therapists, who will remain blinded to treatment assignment. To further protect the blinding of the Assessing Therapist, subjects will be reminded not to discuss with the Assessment Therapist any details of their six weeks of therapy. The assessments to be performed include FM Scale, Box & Blocks Test, Stroke Knowledge Exam, and Stroke Impact Scale-Hand Subsection. Additionally, the Assessment Therapist will record adverse events (which includes study-related adverse events, serious adverse events, and interval medical history), document any new medications and will document the amount of any therapy (OT, PT, SLT) that the subject received outside of study procedures.

